13. EXPLORATORY ANALYSES

An MMRM model will be used to evaluate differences between treatment groups in the change from baseline in pre-dialysis serum levels of hs-CRP after each 4 weeks of treatment. The model will include the fixed effect of treatment, visit, as well as the continuous, fixed covariate of baseline measurement and the random effect of patient.

An MMRM model will be used to evaluate differences between treatment groups in the change from first day of treatment in KDQOL-36 and EQ-5D-5L after 12 weeks and after 24 weeks of treatment. The model will include the fixed effect of treatment, visit, as well as the continuous, fixed covariate of screening measurement and the random effect of patient.

Cumulative doses in the utilization for medications (i.e., ESA, anti-hypertensive, iron and phosphate) over 4 weeks intervals across 24 weeks study treatment will be summarized descriptively. An MMRM model will be used to evaluate differences between treatment groups in the change from accumulation of 4 weeks prior to study treatment after 4, 8, 12, 16, 20 and 24 weeks study treatment. The analysis of the exploratory endpoints will be carried out on the FAS.

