8.5.1 Visit Procedures

Clinical laboratory evaluations will be taken at the first study dialyzer treatment and after every 4 weeks of treatment (i.e., Day 1 [first day of treatment], Week 4, Week 8, Week 12, Week 16, Week 20 and Week 24).

On the day of the study visit, the following dialysis treatment data will be collected:

- Treatment parameters:
 - Programmed Q_B , Q_D and ultrafiltration flow rate (Q_{UF}); (all in mL/min)
 - Actual Total Ultrafiltration volume at end of treatment (mL/Session)
 - Q_B will be documented at the start, every 30 minutes, and at the end of every study treatment
 - Total dialysis time
- Duration of and reasons for any treatment interruptions
- Concomitant medications
- AEs/SAEs/ADEs/PCs
- PRO measurements (KDQOL-36 and EQ-5D-5L)
- Vital signs
- Pre- and post-dialysis body weight
- Clinical laboratory evaluation as outlined in [Appendix 2](#)

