5.2 Baseline Definition

Baseline measure for laboratory assessments and vital signs is defined as the last predialysis non-missing value obtained prior to dialysis on the day of the first study treatment. The final measure for laboratory assessments is defined as the last value captured during study treatment sessions (Week 24). If laboratory assessment on Week 24 is not applicable, the value on end of study visit (pre-dialysis) will be considered as final measurement.

Baseline measure for demographics, physical examination, general medical history and renal medical history is obtained during screening.

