^c AEs, SAEs and PCs will be collected after the informed consent is signed and throughout the study, until the end of study visit. ADEs will be collected throughout the treatment period.

^d Medications will be collected throughout the study.

^e Ultrafiltration (U_F) will be obtained at the end of treatment of each 4 weeks treatment period.

^f Collection of laboratory samples is presented in the Schedule of Clinical Laboratory Evaluations below.

^g Patient reported outcomes (PROs) will include KDQOL-36 and EQ-5D-5L. All PROs will initially be assessed during the first treatment day, after 12 weeks of treatment and at the end of the study, following 24 weeks of treatment.

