5.8 Exploratory Measures

Exploratory assessments include:

- Inflammatory marker high-sensitivity C-Reactive protein (hs-CRP) measured predialysis on the first day of treatment and after every 4 weeks of treatment.
- KDQOL-36 measured on the first day of treatment, after 12 weeks and after 24 weeks of treatment.
- EQ-5D-5L measured on the first day of treatment, after 12 weeks and after 24 weeks of treatment.
- Changes in utilization for medication as cumulative dose for every 4 weeks' interval (i.e., erythropoiesis-stimulating agent (ESA), anti-hypertensive, iron and phosphate).

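### The KDQOL-36 and EQ-5D-5L models adjust for a screening value that the schedule does not collect, so the between-group analysis cannot be run as written

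*SAP*

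**What the plan says.** SAP section 13 models the "change from first day of treatment in KDQOL-36 and EQ-5D-5L after 12 weeks and after 24 weeks of treatment". The fixed effects are treatment and visit, and the model adds a "fixed covariate of screening measurement and the random effect of patient". Protocol 10.7 and the exploratory paragraph of the protocol synopsis give the same model with the same covariate.

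The collection times are stated separately. SAP 5.8 lists "KDQOL-36 measured on the first day of treatment, after 12 weeks and after 24 weeks of treatment" and "EQ-5D-5L measured on the first day of treatment, after 12 weeks and after 24 weeks of treatment"; Protocol 3.2.3 agrees. Footnote g to the visit schedule (SAP Table 1 and Protocol Appendix 1) reads "All PROs will initially be assessed during the first treatment day, after 12 weeks of treatment and at the end of the study".

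SAP 5.2 defines baseline for laboratory tests and vital signs as the pre-dialysis value on the first treatment day. It then says "Baseline measure for demographics, physical examination, general medical history and renal medical history is obtained during screening". It gives no baseline for the two questionnaires.

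**The concern.** The outcome is measured from one time point and the covariate is taken from another, and the second does not exist in the schedule. A standard mixed model omits any record with a missing covariate, so here it would omit all of them.

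Quality of life is one of two exploratory objectives (Protocol 2.3, SAP 4.3), and this is the only between-group model specified for it. Someone will have to choose a different covariate, or none, once the programming starts. In an open-label trial that choice is better written down before results by treatment are available. The choice also affects precision: leaving the covariate out costs some efficiency compared with adjusting for the first-day value.

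**Working it through.** **Step 1. Is there a screening questionnaire anywhere?** The relevant places, side by side:

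| Place | What it shows for KDQOL-36 and EQ-5D-5L |
|---|---|
| SAP 13, Protocol 10.7, synopsis | Covariate is a screening value |
| SAP Table 1, Protocol Appendix 1 | Screening cell empty; Visit 1 pre-dialysis cell empty; marked post-dialysis at Visit 1, Week 12 and Week 24 |
| Footnote g to both tables | First assessment is on the first treatment day |
| SAP 5.8, Protocol 3.2.3 | First treatment day, Week 12, Week 24 |
| Protocol 8.4.1 (screening procedures) | Not listed |
| Protocol 8.5.1 (treatment visits) | Listed, with no pre- or post-dialysis order |
| SAP 5.2 (baseline) | Not mentioned |
| SAP 10 (changes from protocol) | Not mentioned |

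The schedule row has 16 columns. The marks fall in columns 3, 9 and 15; column 1 is screening. Scheduled screening questionnaires: 0. The empty cell is not a table-extraction fault, because footnote g and the endpoint lists say the same in prose.

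**Step 2. Can the text be read another way?** Because SAP 5.2 gives the questionnaires no baseline, the screening covariate cannot be resolved through a definition. The hs-CRP model in the same section of the SAP adjusts for the baseline measurement, so the wording here differs from its neighbour. SAP 10 corrects a mis-transcribed protocol formula but leaves this covariate alone.

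**Step 3. What would dropping the covariate cost?** The documents give no correlation between questionnaire scores over time, so r is an assumption, taken as 0.5 to 0.7. Consider one post-baseline visit, with variance s² at both times:

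- Unadjusted change score: variance 2(1 − r)s²
- Change score adjusted for the first-day value: variance (1 − r²)s²
- Ratio, adjusted to unadjusted: (1 − r²) / [2(1 − r)] = (1 + r)/2

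| Assumed r | Unadjusted change | Adjusted | Ratio | Reduction forgone |
|---|---|---|---|---|
| 0.5 | 1.00 s² | 0.75 s² | 0.75 | 25% |
| 0.7 | 0.60 s² | 0.51 s² | 0.85 | 15% |

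The loss shrinks as the correlation rises, because taking the difference already removes most of the shared variation. There is no figure in the plan to reproduce; no sample size or power statement concerns these endpoints.

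**The case against.** The best reply is that little hangs on this. The endpoints are exploratory and lie outside both the primary gate and the eight-step secondary hierarchy. The intended covariate is easy to guess, since the outcome already requires the first-day value. The error would also show itself at once as an empty model rather than bias a result unnoticed, and the study statistician is blinded to treatment (Protocol 5.5). All of this stands and limits the weight of the point. It does not remove it: three places name a variable that is not scheduled, and an analysis plan should not depend on a guess.

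Three stronger readings are tempting, and the documents do not support them.

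- A reader might infer that quality of life is left with no analysis at all. SAP 7.1 provides descriptive summaries of continuous data, and SAP 7.6.1 and 7.6.2 specify how both questionnaires are scored. Only the between-group model fails.
- A reader might put the precision at stake at 25% to about 50%, using 1 − r² = 0.75 at r = 0.5 and 0.51 at r = 0.7. That compares adjustment with unadjusted Week 24 scores, which the plan does not analyse. The planned outcome is change, so the 15% to 25% range above applies.
- A reader might infer that the Day 1 questionnaires are certainly completed after the first study session. The tables mark the post-dialysis column, but footnote g says only that it is that day, and Protocol 6.6 and 8.5.1 set no order. What can be said is that they are scheduled post-dialysis.

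**Conclusion.** The point holds. The between-group model for KDQOL-36 and EQ-5D-5L names a covariate with no scheduled measurement in any patient, and it cannot be run as specified in SAP 13, Protocol 10.7 or the synopsis. That conclusion rests on the documents alone and needs no assumption about correlation.

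Its reach is limited to exploratory endpoints. The cost of the simplest workaround, dropping the covariate, is a forgone variance reduction of about 25% at r = 0.5 or 15% at r = 0.7. Those figures assume the stated correlations, equal variances and a single follow-up visit; the planned model uses two visits, so they are a guide to size only.

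One matter needs disclosure whichever wording is adopted. Randomization takes place at the end of screening (footnote b to the schedule), and the first questionnaire is scheduled post-dialysis at Visit 1. As scheduled, the reference value therefore follows allocation and the first study session. The documents do not show that this distorts the comparison, but a reader of the results should know it.

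**What to change.** 1. In SAP 13, Protocol 10.7 and the exploratory paragraph of the protocol synopsis, replace the screening covariate with the first-day-of-treatment measurement, the same value from which change is calculated. Changing only the two main sections would leave the protocol contradicting its own synopsis.
2. In SAP 5.2, add a baseline definition for KDQOL-36 and EQ-5D-5L: the first-treatment-day value, noting that the Visit 1 questionnaires are scheduled post-dialysis.
3. If the protocol will not be amended again, record the correction in SAP 10, alongside the formula correction already listed there.

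The cost is a few words in three places and one added sentence. The first-day value is already scheduled, so there is no new data collection and no effect on sample size, power or the testing hierarchy.

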Appendix 1 Formulas for Calculation of Endpoints Reduction Ratios (RR)

The RR for each solute, based on the change in the arterial plasma concentration over the dialysis session, will be calculated as:

$$RR (\%) = \left(1 - \frac{C_{Post}}{C_{Pre}}\right) \times 100$$

where C_{Pre} and C_{Post} are measured arterial plasma concentration of the solute before and after dialysis, respectively.¹

However, for the middle molecules (λ FLC and β_2 -microglobulin) C_{Post} will be first corrected (C_{Post-corr}) for the decrease in total extracellular volume due to fluid removal, as follows:

$$C_{Post-corr} = \frac{C_{Post}}{(1 + \frac{BW_{Pre} - BW_{Post}}{0.2 \times BW_{Post}})}$$

where C_{Post} is the measured plasma concentration of the solute after dialysis; and BW_{Pre} and BW_{Post} are the patient's body weight before and after dialysis, respectively.²

Kt/Vurea (quantification of hemodialysis treatment adequacy)

The linear equation used to calculate Kt/V_{urea} when applied to HD administered 3 times a week is as follows:

$$\frac{Kt}{V} = -\ln(R - 0.008 \times T) + (4 - 3.5 \times R) \times 0.55 \times \frac{Weightloss}{V}$$

where R is the ratio of post-dialysis to pre-dialysis BUN; V is the body water volume and Weightloss is expressed in the same units; and T is treatment time in hours.³⁴

¹ Krieter DH, Lemke HD, Wanner C. A new synthetic dialyzer with advanced permselectivity for enhances low-molecular weight protein removal. *Artif Organs*. 2008;32(7):547-554.

² Bergström J, Wehle B. No change in corrected β 2-microglobulin concentration after cuprophane haemodialysis. *Lancet.* 1987;1:628-629.

³ National Kidney Foundation. KDOQI Clinical Practice Guideline for Hemodialysis Adequancy: 2015 Update. *Am J Kidney Dis.* 2015;66(5):884-930.

⁴ Daugirdas JT. Second generation logarithmic estimates of single-pool variable volume Kt/V: an analysis of error. *J Am Soc Nephrol.* 1993;4(5):1205-1213.

nPNA (nPCR)

The below equations are used to calculate the midweek nPNA (PCR) when applied to HD patients is as follows:

$$nPNA (PCR) = \frac{C_0}{\left[25.8 + 1.15 \times \frac{spKt}{V} + \frac{56.4}{\frac{spKt}{V}}\right]} + 0.168$$

where C_0 is the pre-dialysis BUN.

SpKt/V is calculated as per below equation:

$$\frac{spKt}{V} = -Ln(R - 0.008 \times t) + (4 - (3.5 \times R)) \times \frac{UF}{W}$$

where R is the post-dialysis/pre-dialysis BUN in mg/dL, t is the dialysis session in hours, UF is the ultrafiltration volume in liters, and W is the post-dialysis weight in kilograms, height in centimeters.⁵

V is calculated as per Watson formulas below:

$$Males V = 2.447 - (0.09516 \times age) + (0.1074 \times height) + (0.3362 \times weight)$$

Females
$$V = -2.097 + (0.1069 \times height) + (0.2466 \times weight)$$

where V is the total body water.⁶

⁵ Depner TA, Daugirdas T. Equations for Normalized Protein Catabolic Rate Based on two-Point Modeling of Hemodialysis Urea Kinetics. *J Am Soc Nephrol.* 1996;7:780-785.

⁶ National Kidney Foundation. NKF_DOQI Clinical Practice Guidelines: Measurement of dialysis adequacy. *Am J Kidney Dis.* 1997;30(2):S22-S31.

Appendix 2 Exposure-Adjusted Incidence Rate

Exposure-adjusted incidence rate (EAIR), defined as the number of subjects with a specific event divided by the total exposure-time among the subjects in the treatment group and at risk of an initial occurrence of the event^{7,8}, Specifically,

$$EAIR = \frac{n}{T} = \frac{n}{\sum t_i}$$

where *n* is the number of subjects with events, t_i is a subjec's exposure time under a given unit and *T* is the total exposure time under a given time unit of the subject. If a subject has multiple events, the t_i is the time of the first event. For a subject with no event, the t_i is censored at the last follow-up time for that subject. The definition of EAIR is based on the assumption that the occurrences of a specific event are following an independent Poisson process, so the event occurs with a constant rate over time.

Use the same 2×2 contingency table as before, the test statistic is given by

$$E = \left(\frac{n_{11}}{T_1} - \frac{n_{12}}{T_2}\right) / \sqrt{\frac{n_{11}}{T_1^2} + \frac{n_{12}}{T_2^2}}$$

Which follow the standard normal distribution under the null hypothesis.

⁷ Liu GF, Wang J, Liu K, Snavely DB. Confidence intervals for an exposure adjusted incidence rate difference with applications to clinical trials. Stat Med. 2006;25(8):1275-1286.

⁸ Cao D, He X. Statistical Analysis of Adverse Events in Randomized Clinical Trials Using SAS. Pharma SUG. Nashville, Tennessee; 2011.

Appendix 3 Clinical Laboratory Evaluation Name Mapping Table 8: Clinical Laboratory Evaluation Name Mapping

| Clinical Laboratory Evaluation Name in Protocol | Clinical Laboratory Evaluation Name in CDSIC |
|---|--|
| АРТТ | Activated Partial Thromboplastin Time |
| Alanine aminotransferase (ALT; SGPT) | Alanine Aminotransferase |
| Serum albumin | Albumin |
| Alkaline phosphatase (ALK-P) | Alkaline Phosphatase |
| Aspartate aminotransferase (AST; SGOT) | Aspartate Aminotransferase |
| Basophils | Basophils |
| Basophils (%) | Basophils (%) |
| β2-Microglobulin | Beta-2 Microglobulin |
| Bicarbonate | Bicarbonate |
| Total Bilirubin | Bilirubin |
| Calcium | Calcium |
| Chloride | Chloride |
| Total Cholesterol | Cholesterol |
| β-hCG | Choriogonadotropin Beta |
| Creatinine | Creatinine |
| Direct Bilirubin | Direct Bilirubin |
| Eosinophils | Eosinophils |
| Eosinophils (%) | Eosinophils (%) |
| Mean corpuscular hemoglobin concentration (MCHC) | Ery. Mean Corpuscular HGB Concentration |
| Mean corpuscular hemoglobin (MCH) | Ery. Mean Corpuscular Hemoglobin |
| Mean corpuscular volume (MCV) | Ery. Mean Corpuscular Volume |
| Red blood cell (RBC) | Erythrocytes |
| Factor VII | Factor VII Activity |
| Protein C | Factor XIV Activity |

I

| Gamma-glutamyl-transferase (GGT) | Gamma Glutamyl Transferase |
|------------------------------------|--|
| Globulin | Globulin |
| Glucose | Glucose |
| HDL cholesterol | HDL Cholesterol |
| Human Immunodeficiency Virus (HIV) | HIV Antigen/Antibody |
| Hematocrit | Hematocrit |
| Hemoglobin | Hemoglobin |
| Hepatitis A Virus (HAV) | Hepatitis A Virus Antibody |
| Hepatitis B Virus (HBV) | Hepatitis B Virus Surface Antigen |
| Hepatitis C Virus (HCV) | Hepatitis C Virus Antibody |
| hs-C-Reactive Protein (hs-CRP) | High-sensitivity C-reactive Protein |
| Indirect Bilirubin | Indirect Bilirubin |
| IL-6 | Interleukin 6 |
| кFLC | Kappa Light Chain, Free |
| κ FLC/ λ FLC ratio | Kappa Lt Chain, Free/Lambda Lt Chain, Free |
| LDL cholesterol | LDL Cholesterol |
| λFLC | Lambda Light Chain, Free |
| White blood cell (WBC) | Leukocytes |
| Lymphocytes | Lymphocytes |
| Lymphocytes (%) | Lymphocytes (%) |
| Monocytes | Monocytes |
| Monocytes (%) | Monocytes (%) |
| Neutrophils | Neutrophils |
| Neutrophils (%) | Neutrophils (%) |
| Serum Phosphorus | Phosphate |
| Platelets | Platelets |
| Potassium | Potassium |

I

| Total Protein | Protein |
|---------------|------------------------------------|
| Factor II | Prothrombin Activity |
| INR | Prothrombin Intl. Normalized Ratio |
| РТ | Prothrombin Time |
| Sodium | Sodium |
| Triglycerides | Triglycerides |
| ΤΝFα | Tumor Necrosis Factor |
| BUN | Blood Urea Nitrogen |
| Vitamin A | Vitamin A |
